16.1 ADVERSE EVENT REPORTING REQUIREMENTS

a. Purpose

Adverse event data collection and reporting, which are required as part of every clinical trial, are done to ensure the safety of participants enrolled in the studies as well as those who will enroll in future studies using similar agents. Adverse events are reported in a routine manner at scheduled times during a trial. (Directions for routine reporting are provided in [Section 14.0](#).) Additionally, certain adverse events must be reported in an expedited manner to allow for more timely monitoring of participant safety and care. The following guidelines prescribe expedited adverse event reporting for this protocol.

b. Reporting method

This study requires that expedited adverse events be reported using the Cancer Therapy Evaluation Program Adverse Event Reporting System (CTEP-AERS). CTEP's guidelines for CTEP-AERS can be found at <http://ctep.cancer.gov>. A CTEP-AERS report must be submitted to the SWOG Operations Office electronically via the CTEP-AERS Web-based application located at: http://ctep.cancer.gov/protocolDevelopment/electronic_applications/adverse_events.htm.

c. When to report an event in an expedited manner

Some adverse events require 24-hour notification (refer to [Table 16.1](#)) via CTEP-AERS.

When the adverse event requires expedited reporting, submit the report within the number of calendar days of learning of the event, as specified in [Table 16.1](#).

In the rare event when internet connectivity is disrupted a 24-hour notification is made to NCI by telephone at [contact]. An electronic report MUST be submitted immediately upon re-establishment of internet connection.

Any supporting documentation should be submitted to CTEP per NCI guidelines for AE reporting located at:

http://ctep.cancer.gov/protocolDevelopment/electronic_applications/docs/aeguidelines.pdf.

d. Other recipients of adverse event reports

The DCTD/NCI will forward reports and documentation to the FDA and drug companies as required

Adverse events determined to be reportable to the Institutional Review Board responsible for oversight of the participant must be reported according to local policy and procedures.

e. **Expedited reporting for investigational agents**

Expedited reporting is required if the participant has received at least one dose of the investigational agents as part of the trial. Reporting requirements are provided in [Table 16.1](#). The investigational agent used in this study is pembrolizumab (MK-3475). If there is any question about the reportability of an adverse event or if on-line CTEP-AERS cannot be used, please telephone or email the SAE Specialist at the Operations Office, [name] or [contact], before preparing the report.

CLOSED EFFECTIVE 05/03/2022

Table 16.1:
Late Phase 2 and Phase 3 Studies: Expedited Reporting Requirements for Adverse Events that Occur on Studies under a CTEP IND within 30 Days of the Last Administration of the Investigational Agent/Intervention¹ pembrolizumab (MK-3475).

FDA REPORTING REQUIREMENTS FOR SERIOUS ADVERSE EVENTS (21 CFR Part 312)				

NOTE: Investigators MUST immediately report to the sponsor (NCI) ANY Serious Adverse Events, whether or not they are considered related to the investigational agent(s)/intervention (21 CFR 312.64)
 
An adverse event is considered serious if it results in ANY of the following outcomes:
 
 1) Death 2) A life-threatening adverse event 3) An adverse event that results in inpatient hospitalization or prolongation of existing hospitalization for ≥ 24 hours 4) A persistent or significant incapacity or substantial disruption of the ability to conduct normal life functions 5) A congenital anomaly/birth defect. 6) Important Medical Events (IME) that may not result in death, be life threatening, or require hospitalization may be considered serious when, based upon medical judgment, they may jeopardize the participant or subject and may require medical or surgical intervention to prevent one of the outcomes listed in this definition. (FDA, 21 CFR 312.32; ICH E2A and ICH E6). 				

ALL SERIOUS adverse events that meet the above criteria MUST be immediately reported to the NCI via CTEP-AERS within the timeframes detailed in the table below.
				
Hospitalization	Grade 1 Timeframes	Grade 2 Timeframes	Grade 3 Timeframes	Grade 4 & 5 Timeframes
Resulting in Hospitalization ≥ 24 hrs	10 Calendar Days			24-Hour 5 Calendar Days
Not resulting in Hospitalization ≥ 24 hrs	Not required		10 Calendar Days	

NOTE: Protocol specific exceptions to expedited reporting of serious adverse events are found in the Specific Protocol Exceptions to Expedited Reporting (SPEER) portion of the CAEPR, Expedited AE reporting timelines are defined as:
 
 ○ "24-Hour; 5 Calendar Days" - The AE must initially be reported via CTEP-AERS within 24 hours of learning of the AE, followed by a complete expedited report within 5 calendar days of the initial 24-hour report. ○ "10 Calendar Days" - A complete expedited report on the AE must be submitted within 10 calendar days of learning of the AE. 				

¹Serious adverse events that occur more than 30 days after the last administration of investigational agent/intervention and have an attribution of possible, probable, or definite require reporting as follows:
 
Expedited 24-hour notification followed by complete report within 5 calendar days for:
 
 • All Grade 4, and Grade 5 AEs 
Expedited 10 calendar day reports for:
 
 • Grade 2 adverse events resulting in hospitalization or prolongation of hospitalization • Grade 3 adverse events 				
May 5, 2011				

f. **Additional Instructions or Exceptions to CTEP-AERS Expedited Reporting Requirements for Late Phase 2 and Phase 3 Studies Utilizing an Agent under a CTEP IND:**

1. Group-specific instructions

Submission of the on-line CTEP-AERS report plus any necessary amendments generally completes the reporting requirements. In addition, you may be asked to submit supporting clinical data to the Operations Offices in order to complete the evaluation of the event. If requested, the supporting data should be sent within **5 calendar days** by fax to [contact] and [contact]. Supporting clinical data submitted should include:

- Printed copy of the first page of the CTEP-AERS Report.
- Copies of clinical sourced documentation of the event.
- If applicable, and they have not yet been submitted to the SWOG Data Operations Center copies of Off Treatment Notice and/or Notice of Death.

g. Reporting Secondary Malignancy, including AML/ALL/MDS

1. A secondary malignancy is a cancer caused by treatment for a previous malignancy (e.g., treatment with investigational agent/intervention, radiation or chemotherapy). A secondary malignancy is not considered a metastasis of the initial neoplasm.

CTEP requires all secondary malignancies that occur following treatment with an agent under an NCI IND to be reported via CTEP-AERS. Three options are available to describe the event.

- Leukemia secondary to oncology chemotherapy (e.g., Acute Myelocytic Leukemia [AML])
- Myelodysplastic syndrome (MDS)
- Treatment-related secondary malignancy

Any malignancy possibly related to cancer treatment (including AML/MDS) should also be reported via the routine reporting mechanisms outlined in each protocol.

Second Malignancy: A second malignancy is one unrelated to the treatment of a prior malignancy (and is NOT a metastasis from the initial malignancy). Second malignancies require ONLY routine reporting via CDUS unless otherwise specified.

For more information see:

http://ctep.cancer.gov/protocolDevelopment/electronic_applications/docs/aeguidelines.pdf.

2. Any supporting documentation should be submitted to CTEP per NCI guidelines for AE reporting located at:

http://ctep.cancer.gov/protocoldevelopment/electronic_applications/aeguidelines.pdf.

A copy of the report and the following supporting documentation must also be submitted to SWOG Operations Office within 30 days by fax to [contact] or mail to the address below:

- a copy of the pathology report confirming the AML/ALL /MDS diagnosis
- (if available) a copy of the cytogenetics report

SWOG
ATTN: SAE Program
[name]
[name]

NOTE: If a participant has been enrolled in more than one NCI-sponsored study, the report must be submitted for the most recent trial.

h. **Reporting Pregnancy, Fetal Death, and Death Neonatal**

1. **Pregnancy** Study participants who become pregnant while on study; that pregnancy should be reported in an expedited manner via CTEP-AERS as **Grade 3 “Pregnancy, puerperium and perinatal conditions – Other (pregnancy)”** under the **Pregnancy, puerperium and perinatal conditions SOC**.

Additionally, the pregnancy outcome for participants on study should be reported via CTEP-AERS at the time the outcome becomes known, accompanied by the same Pregnancy Report Form used for the initial report.

2. **Pregnancy Loss** Pregnancy loss is defined in CTCAE as “Death in utero.” Pregnancy loss should be reported expeditiously as **Grade 4 “Pregnancy loss”** under the **Pregnancy, puerperium and perinatal conditions SOC**.

A Pregnancy loss should **NOT** be reported as a Grade 5 event under the Pregnancy, puerperium and perinatal conditions SOC, as currently CTEP-AERS recognizes this event as a participant death.

3. **Death Neonatal** “Death neonatal is defined in CTCAE as “Newborn death occurring during the first 28 days after birth” that is felt by the investigator to be at least possibly due to the investigational agent/intervention should be reported expeditiously. A neonatal death should be reported expeditiously as **Grade 4, “Death neonatal”** under the **General disorders and administration SOC**.

*Fetal death and neonatal death should **NOT** be reported as a Grade 5 event. If reported as such, the CTEP-AERS interprets this as a death of the participant being treated.*

NOTE: When submitting CTEP-AERS reports for “Pregnancy, “Pregnancy loss”, or “Neonatal loss”, the Pregnancy Information Form should also be completed and faxed with any additional medical information to [contact]. The potential risk of exposure of the fetus to the investigational agent(s) or chemotherapy agent(s) should be documented in the “Description of Event” section of the CTEP-AERS report.

The Pregnancy Information Form is available at
http://ctep.cancer.gov/protocolDevelopment/adverse_effects.htm.

18.1 Surgical Management Guidelines

a. Excision of the Primary Site

These guidelines apply to participants presenting with an intact primary and planning for a lymph node dissection as their surgical procedure.

Primary Tumor: All such participants must undergo adequate wide excision of the primary tumor meeting the suggested criteria outlined below, if not already completed. In most cases, this must be a wide excision with 1 cm minimum margins. In all cases, the margins of excision must be histologically free of melanoma (including melanoma in-situ or atypical junctional melanocytic hyperplasia). For all sites except head & neck and extremities distal to the wrist or ankle, the primary melanoma must be excised with at least 1 cm margins of normal skin in all directions, measured either from the edge of the primary tumor or from the edge of the biopsy scar if prior excisional biopsy has been done. The excision should go down to the fascia; including the fascia in the resection is optional. Measurements of margins should ideally be done by the surgeon at the time of wide excision using a ruler; if the measurement is done by the pathologist, allowance of 33% for shrinkage will be made. In addition to the gross margin, a histologically negative margin (including histologic freedom from atypical junctional melanocytic hyperplasia) must be obtained.

For primary melanomas on the head & neck or extremities distal to the wrist or ankle, the primary melanoma must be excised and a histologically negative margin (including histologic freedom from atypical junctional melanocytic hyperplasia) must be obtained. Measured margins of at least 1 cm are desirable, but not mandatory. Acral-lentiginous melanomas (including subungual primaries) may be resected by any procedure that yields a histologically negative margin, including amputation and digit-conserving surgery.

b. Excision of Recurrent Disease

All participants enrolled with regional disease, including recurrence after initial presentation, must have clinically detectable, surgically resectable disease (regional or distant disease). Participants presenting with satellite metastases (within 2 cm of the primary) or in transit metastases (beyond 2 cm from the primary but proximal to the regional lymph nodes) are eligible provided that they have been deemed surgically resectable by a surgeon, and they have NOT undergone prohibited systemic therapy for their satellite/in transit metastases (see [Section 5.1b](#)).

c. Regional Lymph Nodes

Regional lymph node dissection is mandatory for all participants with histologic or clinical evidence of regional lymph node involvement enrolled on this trial. (Participants with satellite/in transit disease and no evidence of nodal involvement may be enrolled without lymph node dissection.) The node dissection must be done in accord with the following guidelines; lymph node sampling is not acceptable. Sentinel lymph node biopsy alone, without completion lymph node dissection, is not acceptable.

The number of tumor-involved nodes must be documented for all cases. Either H&E or immunohistochemical evidence of involvement is acceptable for determining the number of involved nodes, but RT-PCR or other molecular techniques are not. Participants with confluent nodal involvement that makes determination of the exact number of involved nodes difficult are eligible and are considered to have "matted nodes" and classified as N3.

1. Cervical Lymph Node Dissection

A classic radical neck dissection is not required and is discouraged. Preservation of the internal jugular vein, sternocleidomastoid muscle, and eleventh cranial nerve ("functional neck dissection") should be performed whenever possible. Consideration should be given to the parotid gland nodes, particularly for melanomas of the face, anterior ear and temporal region, which should be removed by total parotidectomy if there is evidence of involvement by tumor. The facial nerve (seventh cranial nerve) should be spared unless invaded by tumor.

2. Axillary Lymph Node Dissection

Removal of at least the level I and II axillary lymph nodes is the minimum acceptable operation. Level III nodes must be removed if clinically suspicious. The minimum borders of the dissection are the latissimus dorsi muscle laterally, the axillary vein superiorly, and the medial border of the pectoralis minor muscle medially. The nerves to the serratus anterior (long thoracic nerve) and latissimus dorsi (thoracodorsal nerve) should be identified and preserved if possible. If the primary tumor is on the trunk, consideration should be given to remove the low axillary nodes (at or below the level of the nipple) by following the latissimus dorsi muscle down to its origin on the chest wall and dissecting the node-bearing tissue between it and the serratus anterior muscle.

3. Inguinal or Ilioinguinal Lymph Node Dissection

The minimum operation for groin node dissections is a superficial inguinal lymph node dissection (inguinal or inguinofemoral lymphadenectomy). A pelvic (iliac and obturator) node dissection is also necessary (ilioinguinal lymphadenectomy) if these nodes are felt to be involved by imaging studies or intraoperative palpation. The borders of a superficial inguinal lymph node dissection are the adductor muscles medially, the sartorius laterally, the junction of these two muscles caudally, the femoral vessels posteriorly, and a line connecting the pubic tubercle and the anterior superior iliac spine superiorly. The node-bearing tissue superficial to the external oblique fascia and superior to the inguinal ligament should be included with the specimen, up to the level of this line. Removal of the pelvic nodes, if required, may be accomplished through the same or a separate incision. Minimally invasive surgical approaches, such as robotic-assisted pelvic lymphadenectomy, are acceptable provided the operation otherwise conforms to the standards described.

d. Other Sites of Nodal Involvement

Lymph node dissections at sites other than those mentioned (e.g., popliteal or epitrochlear) should be carried out only if involvement of the nodes with melanoma is documented or if the primary site lies directly over the node group and node dissection is necessary to allow adequate wide excision. Participants with nodal involvement in these sites, as well as those with recurrent disease in the regional nodal basin after a previous complete lymphadenectomy, are eligible for this trial.

e. Resection of Distant Metastatic Disease

Participants with Stage IV melanoma metastatic to skin, subcutaneous sites, distant lymph nodes or lung or other visceral sites are allowed provided sites are resectable per surgical note source document and they have NOT undergone prohibited systemic therapy for their metastatic disease (see [Section 7.2](#)) and the participant otherwise meets the eligibility criteria outlined in [Section 5.0](#). Participants with resected brain metastases are not eligible. Minimally invasive surgical approaches, such as video-assisted thoracotomy, are acceptable. Failure to document the margin status may lead to the participant being declared ineligible. Stereotactic radiosurgery or ablative techniques that do not involve resection of the tumor to negative margins are not acceptable.

CLOSED EFFECTIVE 03/2022

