5.0 ELIGIBILITY CRITERIA

Each of the criteria in the following section must be met in order for a patient to be considered eligible for randomization. For each criterion requiring test results and dates, please record this information on the Onstudy Form and submit via Medidata Rave® (see [Section 14.0](#)). Any potential eligibility issues should be addressed to the Data Operations Center in Seattle at [contact] prior to randomization. NCI policy does not allow for waiver of any eligibility criterion (http://ctep.cancer.gov/protocolDevelopment/policies_deviations.htm).

In calculating days of tests and measurements, the day a test or measurement is done is considered Day 0. Therefore, if a test is done on a Monday, the Monday 2 weeks later would be considered Day 14. This allows for efficient patient scheduling without exceeding the guidelines. **If Day 28, 30, 42 or 84 falls on a weekend or holiday, the limit may be extended to the next working day.**

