5.3 STEP 3 REGISTRATION (Adjuvant Therapy)

- a. Patients must have undergone surgery prior to Step 3 registration. The Step 2 surgery must have completely resected their melanoma.
 - Patients with gross positive residual disease following surgery do not qualify as having disease-free status, and, therefore, such patients are not eligible to register for adjuvant therapy.
 - Patients with microscopic residual disease (i.e., positive margins) can be treated with re-excision or radiation, per site discretion, to render the patient disease-free prior to registration of adjuvant therapy.
 - Disease-free status must be documented by a complete physical examination and radiographic imaging studies within 42 days prior to Step 3 registration. Imaging studies must include a CT of the chest, abdomen, and pelvis (unless contraindicated). Extremity melanomas must be imaged using CT with intravenous contrast or MRI with and without gadolinium. CT imaging must be done with intravenous contrast if there are no contraindications for it.
 - For patients with melanoma arising from the head and neck, dedicated neck imaging (CT with IV contrast, unless contraindicated) is required.

- If the patient has had unknown primary with disease in the axilla, neck imaging is required to assure the region is clear of cancer.
 - Any other clinically indicated imaging studies if performed (e.g., bone scan) must show no evidence of disease.
- b. Patients must be registered to Step 3 no more than 84 days after date of Surgery.
- c. Patients with R0 or R1 resections must have disease-free status documented by a complete physical examination and imaging studies within 42 days prior to Step 3 Registration. These patients must have disease assessment by CT chest/abdomen/pelvis with IV contrast, and neck CT with IV contrast if primary head and neck melanoma. MRI combined with non-contrast CT is an acceptable alternative for patients with CT contrast allergy.
- d. Patients with R2 resections are not eligible for Step 3 and must be removed from study treatment per [Section 7.4](#).

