7.2 Treatment

a. Pre- pembrolizumab (MK-3475) Labs

Blood collected for pretreatment laboratory tests must be collected and analyzed no more than 3 days prior to dosing.

b. Surgery

Participants must undergo surgical resection (lymphadenectomy or resection of in-transit or distant metastasis +/- wide local excision, if applicable) of clinically detectable melanoma. **Timing of surgery is dependent on treatment arm.**

For all participants, the **S1801 Planned Surgery Form** must be filled out prior to randomization and the **S1801 Post-Surgery Form** filled out post-surgery. Submit forms as indicated in [Section 14.0](#).

Pembrolizumab (MK-3475) timing after surgery is up to the discretion of the local investigator. Interval between surgery and start of adjuvant therapy should not exceed 84 days.

c. **Arm 1: Pembrolizumab (MK-3475) Adjuvant Arm**

Step 1: RANDOMIZATION

Participants will be randomized.

Step 2: SURGERY

Participants on Adjuvant arm must be registered to Step 2 (Surgery) within 17 days (preferably within 14 days) after randomization and must undergo surgical resection within 17 days (preferably within 14 days) after Step 2 registration. Radiation is allowed after surgery. **However, interval between Surgery and the start of Adjuvant therapy must not exceed 84 days.**

Step 3: ADJUVANT THERAPY

It is recommended that participants be registered to and initiate treatment on Step 3 (Adjuvant therapy) within 17 days (preferably within 14 days) after surgery. Radiation is allowed after surgery. However, interval between Surgery and start of Adjuvant therapy must not exceed 84 days.

Agent	Dose	Schedule	Route
MK-3475 (pembrolizumab)	200 mg	IV over 30 minutes	Day 1, Q 3 weeks for 18 doses

Pembrolizumab (MK-3475) treatment should be administered after all procedures and assessments have been completed. Pembrolizumab (MK-3475) treatment may be administered up to 3 days before or after the protocol-specified Q 3 weeks due to administrative reasons.

Pembrolizumab (MK-3475) treatment will be administered on an outpatient basis.

Pembrolizumab (MK-3475) will be administered as a 30-minute IV infusion. Infusion timing should be as close to 30 minutes as possible; however, a window of -5 minutes and +10 minutes is permitted (*i.e.*, infusion time is 25-40 minutes).

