Dosing interruptions are permitted in the case of medical/surgical events or logistical reasons not related to study therapy (e.g., elective surgery, unrelated medical events, participant vacation, and/or holidays). Participants should be placed back on study therapy within 3 weeks of the scheduled interruption, unless otherwise discussed with the Study Chairs. The reason for interruption should be documented in the participant's study record.

All planned doses must be administered. Missed doses must be made up.

CLOSED EFFECTIVE 05/05/2022

d. **Arm 2: Pembrolizumab (MK-3475) Neoadjuvant Arm**

Step 1: RANDOMIZATION AND NEOADJUVANT THERAPY

Agent	Dose	Route	Schedule
MK-3475 (pembrolizumab)	200 mg over 30	IV for 3 doses minutes	Day 1, Q 3 weeks followed by surgical resection.

Participants will receive 3 doses of pre-operative (MK-3475) pembrolizumab. Administration of less than 3 doses of pre-operative pembrolizumab (MK-3475) may be allowed in cases of progressive disease requiring surgery or due to toxicity. This must be discussed with the Study Chair for approval. No additional doses of pre-operative pembrolizumab (MK-3475) treatment beyond 3 doses may be given.

Pembrolizumab (MK-3475) treatment should be administered after all procedures and assessments have been completed. Pembrolizumab (MK-3475) treatment may be administered up to 3 days before or after the protocol-specified Q 3 weeks due to administrative reasons.

Pembrolizumab (MK-3475) treatment will be administered on an outpatient basis.

Pembrolizumab (MK-3475) will be administered as a 30-minute IV infusion. Infusion timing should be as close to 30 minutes as possible; however, a window of -5 minutes and +10 minutes is permitted (*i.e.*, infusion time is 25-40 minutes).

Dosing interruptions are permitted in the case of medical / surgical events or logistical reasons not related to study therapy (e.g., elective surgery, unrelated medical events, participant vacation, and/or holidays). Participants should be placed back on study therapy within 3 weeks of the scheduled interruption, unless otherwise discussed with the Study Chairs. The reason for interruption should be documented in the participant's study record.

All planned doses must be administered. Missed doses must be made up.

Step 2: SURGERY:

Surgery should be arranged prior to Step 2 registration. It is recommended that participants undergo Surgery within 3 weeks after the last dose of pembrolizumab (MK-3475).

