11.3 Sample size re-design

Because accrual to the study has been slower than anticipated, it is expected that 100% of events may be reached before accrual to the study completes, and so the total sample size of the study will be adjusted as follows.

To account for the slower than anticipated accrual rate, a total of 336 eligible, randomized patients will be accrued. If up to 1.5% of patients are not eligible, up to 342 patients will be registered. With the same assumptions for EFS as in the original design, this design should have the same power as the original design using the same alpha. We expect to reach full events within 6 months of completing accrual.

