11.4 Secondary endpoints and analyses

OS, local/regional control, and disease control will be estimated using the Kaplan-Meier method and compared between arms using log-rank tests and Cox regression models. Fisher's exact test will be used to compare the number of pembrolizumab (MK-3475) doses received by participants on each treatment arm. Pathologic response, RECIST 1.1

response rates, iRECIST response rates will be tabulated for the neoadjuvant arm and exact 95% confidence intervals will be constructed. For each arm, 250 participants will be sufficient to estimate toxicity to within $\pm 6\%$. Any toxicity occurring with at least 1% probability is likely to be seen at least once (99% probability).

Primary analyses will all be intent-to-treat. We will perform additional analyses per protocol, to understand how variation in treatment in the neoadjuvant arm can impact the analyses.

CLOSED EFFECTIVE 05/05/2022

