14.0 DATA SUBMISSION SCHEDULE

14.1 Data Submission Requirement

Data must be submitted according to the protocol requirements for **ALL** participants registered, whether or not assigned treatment is administered, including participants deemed to be ineligible. Participants for whom documentation is inadequate to determine eligibility will generally be deemed ineligible

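### Section 18.1e lets a margin record made after randomization decide eligibility for Stage IV resections, and Section 11.4 does not say whether such patients stay in the EFS analysis

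*Combined protocol and SAP*

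**What the plan says.** Section 18.1e covers resection of distant metastatic disease. It admits Stage IV participants whose sites a surgical note records as resectable, and then states: "Failure to document the margin status may lead to the participant being declared ineligible". Sections 18.1a and 18.1c set margin and node-documentation requirements for primary and nodal disease but attach no such consequence.

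Section 5.0 ties eligibility to the point of randomization: "Each of the criteria in the following section must be met in order for a patient to be considered eligible for randomization". Section 5.1 contains no margin criterion.

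Under Section 7.2, surgery comes after randomization on both arms. Adjuvant-arm participants register to Step 2 within 17 days of randomization and "must undergo surgical resection within 17 days (preferably within 14 days) after Step 2 registration". On the other arm, before surgery, "Participants will receive 3 doses of pre-operative (MK-3475) pembrolizumab".

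Section 5.3 has a separate, later eligibility step that does depend on the resection: "Patients with R2 resections are not eligible for Step 3". Section 10.10 gives participants on either arm who never register for adjuvant therapy an EFS event at 84 days.

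On numbers, Section 11.3 says that "a total of 336 eligible, randomized patients will be accrued", with up to 342 registered. On the analysis set, Section 11.4 says "Primary analyses will all be intent-to-treat" and defines it no further. Section 14.1 requires data from ineligible participants and adds: "Participants for whom documentation is inadequate to determine eligibility will generally be deemed ineligible". It does not say how those participants are analysed.

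**The concern.** Eligibility for a randomized comparison should rest on facts fixed before assignment. Here it can turn on a record created afterwards, at an operation whose timing depends on the arm.

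Only participants who reach surgery can fail this rule, and the routes to surgery differ. A neoadjuvant participant may progress before the operation (Section 10.4). A neoadjuvant responder may decline surgery without an EFS event if the response is confirmed as Section 10.10 requires; the adjuvant arm has no such exception. Section 12.1 has the surgical chair review operative notes and pathology reports and does not mention blinding to arm. Removing participants on this basis would be neither random nor clearly neutral between arms.

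What is at stake is bias in the primary EFS comparison more than lost precision. The term ineligible also has two possible meanings, and they treat the same patient in opposite ways.

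**Working it through.** **1. When the margins are known.** Section 18.1e requires the sites to be resectable at entry, so they are still in place and the margins are those of the protocol surgery. On the adjuvant arm that can be up to 17 + 17 = 34 days after randomization. On the neoadjuvant arm it comes after three planned doses given every 3 weeks. In neither case is it baseline information.

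**2. Two readings of ineligible.**

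| Reading | Relevant sections | Effect on the patient |
|---|---|---|
| Ineligible for the trial | 18.1e, 11.3, 14.1 | Not counted among the 336; place in the EFS analysis not stated |
| Ineligible for Step 3 | 5.3, 10.10 | Kept, with an EFS event at 84 days |

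Nearby wording in Section 18.1, which speaks of eligibility for the trial and refers to Section 5.0, leans towards the first reading. The text does not settle it.

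**3. The plan's own figures.** Inputs from Sections 11.2 and 11.3: 336 eligible, 1.5% ineligible, 104 events, average hazard ratio 0.64, two-sided 15% level, 1:1 allocation.

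- Registrations: 336 / (1 − 0.015) = 341.1, rounded up to 342, as stated. The margin is 342 − 336 = 6 patients (6/342 = 1.75%) for every cause of ineligibility.
- Power (Schoenfeld): Φ(|ln 0.64| × √(104/4) − 1.44) = Φ(2.276 − 1.440) = 79.8%, close to the stated 81%.

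Section 11.3 does not restate the event count. I take 104 as still the target, because that section keeps the original EFS assumptions, alpha and power.

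**4. Loss of power (hypothetical).** Suppose exclusions come from both arms and events fall in proportion, 104 × (342 − k)/342:

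| Excluded of 342 | Events | Power |
|---|---|---|
| 0 | 104.0 | 79.8% |
| 6 (1.8%) | 102.2 | 79.3% |
| 10 (2.9%) | 101.0 | 78.9% |
| 17 (5.0%) | 98.8 | 78.2% |
| 34 (9.9%) | 93.7 | 76.4% |

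**5. Bias (hypothetical, one arm only).** Suppose there is no true effect, 52 events occur per arm, and k neoadjuvant participants with events are removed. Approximately, the shift in ln HR is ln((52 − k)/52), its standard error is 2/√(104 − k), and the shift in Z is their ratio.

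- k = 3: ln(49/52) = −0.0594; 2/√101 = 0.199; shift about 0.30.
- k = 5: ln(47/52) = −0.1011; 2/√99 = 0.201; shift about 0.50.

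The critical value is 1.44. The chance of a false result favouring neoadjuvant treatment is 7.5% with no removals. At k = 3 it becomes Φ(0.30 − 1.44), about 12.7%; at k = 5, Φ(0.50 − 1.44), about 17%. Removals from the adjuvant arm would push the other way.

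**The case against.** The strongest reply is that nothing in the protocol removes an ineligible participant from the EFS analysis. Section 11.4 says intent-to-treat, and a sample size counted in eligible patients is a planning figure. A reader might infer that the plan drops these patients; the documents do not say so. What stands against the reply is that adding six registrations to secure 336 eligible patients suggests that ineligible patients do not count towards the analysed number, and no sentence says they are kept.

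A reader might also take the sentence as a rule for every participant. It is not: it sits only in the Stage IV paragraph and says that ineligibility may follow. Section 14.1 does not widen it, since that section concerns eligibility documentation in general and does not mention margins.

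The Step 3 reading is a fair alternative. Under it the patient is retained and has an event, so nobody is excluded. It shows that the wording needs settling, and it does not make the wording safe.

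Controls exist. Section 14.3 requires operative and pathology reports and a post-surgery form, and Section 12.1 provides review of surgical records. These make missing margin status less likely.

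Finally, the bias figures are a worst case: every removed patient is on one arm and had an event, and k = 5 uses nearly the whole allowance for all causes of ineligibility. That is correct. They show sensitivity and do not forecast what will happen. The event split expected under the alternative would give larger shifts, but false-positive risk is a question about the null, so 52 per arm is the proper base.

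**Conclusion.** The sentence is wrong as written, with low exposure. It lets a record made after randomization determine eligibility. Because Section 11.4 leaves the intent-to-treat set undefined for patients later ruled ineligible, it permits a post-randomization exclusion that could depend on the arm. The documents do not show that such an exclusion is planned or has occurred.

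The size is illustrative only. It rests on assumed numbers of removals, all with events and all on one arm, and on 104 events split evenly under the null. A handful of such removals would take up a noticeable part of the distance to the 1.44 threshold. The power cost is about 1.6 percentage points even if 17 of 342 were excluded.

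**What to change.** - **Section 18.1e:** restate missing margin documentation as a protocol deviation with no effect on trial eligibility.
- **Sections 5.3 and 10.10:** reconcile the restated sentence with these, so that it is clear whether missing margin records bear on Step 3 registration and how such a patient enters EFS. Which Step 3 rule applies is for the sponsor to settle.
- **Section 11.4:** state that the primary EFS analysis keeps all randomized participants in their assigned arm, that eligibility is judged only on information from before randomization, and that an eligible-only analysis is a sensitivity analysis.

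The cost is a few sentences. Section 14.1 already requires data on ineligible participants, so no new collection is needed. Power does not suffer: analysing all 342 gives about 104 × 342/336 = 105.9 events and 80.4% power by the same formula, against 79.8% at 104. The analysis set should be fixed before the final analysis so that it cannot be chosen after the results are seen.
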